Efforts to develop better treatments for neonatal seizures are confounded by the need in any drug trial for systematic continuous EEG monitoring, something that is not yet standard of care because of resource constraints. The proposed project would add to knowledge regarding the efficacy of LEV in neonates, while simultaneously addressing the need to find feasible solutions to the difficulties of providing continuous EEG monitoring through new technology.

Should LEV prove an effective medication in this age group, clinical practice would be dramatically improved. We would have a safe, non-toxic treatment option for neonatal seizures with proven efficacy. Developing better systems for neonatal seizure detection will facilitate earlier treatment of neonatal seizures and enable further clinical research in this condition.

Prevalence of Neonatal Seizures:

Measures of the incidence of neonatal seizures vary from 1/1000 live births to 3.5/1000 live births. The most recent US study, in Harris County Texas from 1992 to 1994 concluded that the incidence was 1.8/1000 live births². The National Center for Health Statistics reported in 2009 that there were 4.3 million live births in 2007³. Using the survey data from Harris County, this translates to an incidence of 7740 babies in the US. Estimating the prevalence assuming an average 3-day duration of seizures, 63 neonates experience clinical seizures on any particular day in the US. The true incidence and prevalence figures are in fact likely double these numbers as a number of studies have noted that electrographic seizures without clinical manifestations account for 50% or more of neonatal seizure activity^{4,5}, raising the prevalence of neonatal seizures of all types to 126/ day in the US.

Neonatal Seizures cause Brain Injury:

The outcome of neonatal seizures is poor which differs markedly from seizures occurring in older age groups. 20-30% of infants with neonatal seizures die, 20-30% develop epilepsy outside the neonatal period, and 20-

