40% develop cerebral palsy and/or mental retardation⁶. The most recent prospective long term follow-up of clinical neonatal seizures in the province of Newfoundland reported on all live newborns born between 1990 and 1995. Data was available on 82 of 90 children. In 28 term babies only 45% were normal, 16% died, and 32% were impaired⁶. Whilst much of the mortality and morbidity in neonates with seizures can be attributed to the underlying condition, there is mounting evidence that seizures themselves are harmful, especially in the asphyxiated neonatal brain. Studies in rats show that seizures can damage the developing brain^{7, 8}. McBride et al have demonstrated a strong correlation between the amount of electrographic seizure activity and subsequent morbidity and mortality⁹. Preliminary data also demonstrates an improved outcome with prompt and complete cessation of seizures⁴ and in a recent European controlled trial, treatment of subclinical seizures showed a trend for reduction in seizure duration which was associated with less brain injury on MRI¹⁰. Brain MR spectroscopy in neonates suffering seizures secondary to perinatal asphyxia shows brain injury as a consequence of the seizures¹¹. Recent evidence suggests that neonatal seizures independently contribute to poor outcome at 4 years of age in neonatal hypoxic-ischemic injury¹².

Current AEDs for Neonatal Seizures:

Current treatment relies on medications in use since 1914 (Phenobarbital) and 1938 (phenytoin). These agents are neither effective nor safe. Treatment with Phenobarbital or phenytoin produces cessation of neonatal seizures in less than 50% of infants treated¹. Acute side effects of phenobarbital and phenytoin include hypotension, suppression of respiratory drive, cardiac arrhythmia and sedation. Chronic exposure to phenobarbital may be associated with decreased cognitive ability¹³⁻¹⁵.

Neonatal response to AEDs is different to that of adults:

The neonatal response to AEDs is fundamentally different to that of the adult brain^{5, 16, 17}. Neonatal seizures form a unique subset of pediatric seizures for a number of reasons:

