Subjects randomised to receive LEV will, at the onset of electrographically confirmed seizure activity, receive an intravenous loading dose of LEV of 40mg/kg given over 15 minutes. If electrographic seizures are confirmed to persist or recur more than 15 minutes after the first infusion is complete, a further 20mg/kg load of LEV will be administered IV over 15 minutes. Maintenance LEV at 10 mg/kg/dose will be given IV q8 hours and continued for at least 5 days. If seizures persist or recur more than 15 minutes after the second LEV infusion is complete, a PB loading dose of 20 mg/kg will be administered IV over 15 minutes. If seizures persist or recur more than 15 minutes after the first loading dose of PB is complete, a second 20mg/kg load will be administered IV over 15 minutes. This will result in PB being started within 1 hour of the onset of seizures if and when loading with LEV is ineffective. Patients given any PB loading doses will be started on maintenance PB with 1.5 mg/kg/dose given IV q8 hours and continued at least until the end of the study

Figure 2 details the study flow.

Subjects randomized to the control group will, at the onset of electrographically confirmed seizure activity, receive an intravenous loading dose of PB of 20 mg/kg given over 15 minutes. If electrographic seizures are confirmed to persist or recur more than 15 minutes after the first infusion is complete, a further 20mg/kg load of PB will be administered IV over 15 minutes. Maintenance PB at 1.5 mg/kg/dose will be given IV q8 hours and continued for at least 5 days. If seizures persist or recur more than 15 minutes following the second PB infusion, a 40 mg/kg load of LEV will be administered IV over 15 minutes. If seizures persist or recur more than 15 minutes after the first loading dose of LEV is complete, a second 20mg/kg load of LEV will be administered IV over 15 minutes. Patients given an LEV loading doses will be started on maintenance LEV with 10 mg/kg/dose given IV q8 hours and continued at least until the end of the study.

If electrographic seizures are still apparent following treatment with both LEV and PB, or if they recur during the 5 days during which the study protocol is active, the patient will be considered to have failed the experimental treatment regime and institutional specific standard seizure management will dictate the ongoing

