The study population of treated babies with electrographic seizures and the parallel control group at risk for seizures but with none detected forms an excellent cohort for a neurodevelopmental outcome study and the effect of seizures. This is being planned and I am asking the parents in the consent if they are interested in being contacted for a neurobehavioral follow-up study.

Rationale for study design:

Justification for a phase II study: The objectives of this study are to gain preliminary evidence of efficacy of LEV in neonates, to determine if a definitive phase III trial is warranted, and if so, to obtain sample size estimates for that study. In addition further safety data in this population will be acquired.

Planning is underway for a large definitive phase III randomised controlled trial of the leading potential new treatments for neonatal seizures. If LEV is established as efficacious in neonates, a future study comparing it with other agents such as Phenobarbital alone or Phenobarbital in combination with bumetanide or topiramate is likely. Such a study to compare the current standard of care AED treatment with newer agents will require 300-400 treated subjects. Long term follow-up of subjects will be necessary, since neurodevelopmental outcome will be the relevant primary outcome measure.

Prior to a definitive phase III trial of any promising new treatment for neonatal seizures, efficacy in the neonatal age group must be proven. Prospective data on the efficacy LEV in neonatal seizures are not yet sufficient to justify a phase III trial. The precision of the estimated response rate to LEV obtained in this proposed study will be important in the design of a future comparative trial⁶⁴.

Justification of study design using LEV as first line treatment:

While it is customary to study new AEDs in subjects who have failed standard treatments, this is especially problematic for the setting of neonatal seizures. On the one hand, by studying efficacy in only those neonates who have failed to respond to a first line agent, a group of refractory neonates has been selected, who may not respond to any AED. On the other hand, neonatal seizures typically resolve spontaneously in a significant proportion of subjects. These factors make interpretation of second line efficacy data difficult, and a poor surrogate for first line treatment efficacy data.

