The actual individual concentration data, collection times and dosing histories will be used to create graphs of plasma LEV concentration vs. time for each infant. Median plasma drug concentration vs. time curves will also be generated. Summary statistics (i.e., n, mean, standard deviation, median, minimum, maximum, and coefficient of variation) will be calculated for plasma concentrations for each time point and each dose level. LEV population pharmacokinetic parameters will be determined using the computer program NONMEM (ver. 6 or later). The data will be nested with existing raw infant LEV pharmacokinetic data generated in the preliminary LEV study. Assuming linear pharmacokinetics as suggested by our current pharmacokinetic data, studying 12 subjects at each dosage level will result in 90% confidence intervals for the pharmacokinetic parameters (CL, V and $t_{1/2}$) of +/- 15%. The 90% confidence intervals for the exposure parameters (C_{max} , AUC) will be approximately +/- 20%. The pharmacokinetics will be modeled recognizing the two stages of a nonlinear hierarchical model development. The first stage introduces the structural model (e.g. one compartment open model), the population parameters, individual effects and the within-patient variation. The second portion of the model development recognizes that variation between patients in the pharmacokinetic parameters exists and will attempt to determine covariates that may identify different pharmacokinetic subpopulations. A one-compartment model with first order elimination will be utilized. Alternative structural models will be explored if indicated by the data. The impact of clinical factors and demographic factors (including weight, sex, age, race, serum creatinine, hypothermia and dosing regimen) will be assessed as fixed effects in the model. Nested models will be compared graphically and with a likelihood ratio test.

Analysis Plan for Aim 4: Safety analysis

A Fisher's exact test will be used to compare rates of adverse events, serious adverse events and study discontinuation rates between the LEV and control groups.

Analysis Plan for Aim 5 A: Feasibility of remote continuous EEG monitoring system

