15 minutes after the first infusion is complete, a further 20mg/kg load of LEV will be administered IV over 15 minutes. Maintenance LEV at 10 mg/kg/dose will be given IV q8 hours and continued for at least 5 days. If seizures persist or recur more than 15 minutes after the second LEV infusion is complete, a PB loading dose of 20 mg/kg will be administered IV over 15 minutes. If seizures persist or recur more than 15 minutes after the first loading dose of PB is complete, a second 20mg/kg load will be administered IV over 15 minutes. This will result in PB being started within 1 hour of the onset of seizures if and when loading with LEV is ineffective. Patients given any PB loading doses will be started on maintenance PB with 1.5 mg/kg/dose given IV q8 hours and continued at least until the end of the study. Subjects randomized to the control group will, at the onset of electrographically confirmed seizure activity, receive an intravenous loading dose of PB of 20 mg/kg given over 15 minutes. If electrographic seizures are confirmed to persist or recur more than 15 minutes after the first infusion is complete, a further 20mg/kg load of PB will be administered IV over 15 minutes. Maintenance PB at 1.5 mg/kg/dose will be given IV q8 hours and continued for at least 5 days. If seizures persist or recur more than 15 minutes following the second PB infusion, a 40 mg/kg load of LEV will be administered IV over 15 minutes. If seizures persist or recur more than 15 minutes after the first loading dose of LEV is complete, a second 20mg/kg load of LEV will be administered IV over 15 minutes. Patients given an LEV loading doses will be started on maintenance LEV with 10 mg/kg/dose given IV q8 hours and continued at least until the end of the study.

If electrographic seizures are still apparent following treatment with both LEV and PB, or if they recur during the 5 days during which the study protocol is active, the patient will be considered to have failed the experimental treatment regime and institutional specific standard seizure management will dictate the ongoing management. Without unblinding, it will be evident that all subjects will have received 40mg/kg Phenobarbital and 60mg/kg of LEV at this stage.

*For study flow, see appendix.*

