## 7.5 Analysis of Safety Outcomes

Adverse Event and Serious Adverse Events will be tabulated by randomization group and by drugs received, respectively. Details including seriousness, intensity, causality, withdrawal due to event and outcome will be summarized by frequencies and percentages by randomization group and by drugs received. Fisher's exact tests will be used to compare rates of adverse events, serious adverse events, study discontinuation and deaths between randomization group and by drugs received, respectively.

Findings will be tabulated by randomization group overall and for findings marked as AE and SAE, respectively.

Safety Labs (using DAIDS guidelines) will be presented with shift tables (hour 48 vs baseline) by randomization group and by drugs received, respectively.

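### SAP 7.5 tests safety outcomes by drugs received, groups formed after randomization by failure of the first drug, so those p-values cannot separate drug effect from refractoriness

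*SAP*

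**What the plan says.** SAP 7.5 tabulates adverse events (AEs) and serious adverse events (SAEs) under two groupings. It then applies Fisher's exact test under both, to "compare rates of adverse events, serious adverse events, study discontinuation and deaths between randomization group and by drugs received, respectively". It does not say which drugs-received categories are compared, and it attaches no adjustment or caveat to that grouping. SAP 6.2 makes no multiplicity adjustment.

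The safety test in the Protocol (section 8, Analysis Plan for Aim 4) uses only the randomized groups. It is to "compare rates of adverse events, serious adverse events and study discontinuation rates between the LEV and control groups". The drugs-received test is an addition made in the SAP.

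Which drugs an infant receives is set by response. For the LEV arm, SAP 3.1 says: "If seizures persist or recur more than 15 minutes after the second LEV infusion is complete, a PB loading dose of 20 mg/kg" is given. For the PB arm: "If seizures persist or recur more than 15 minutes following the second PB infusion, a 40 mg/kg load of LEV will be administered IV". The Study Design Summary in Protocol section 8 has the same rules.

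**The concern.** The drugs-received groups are formed after randomization, largely by an outcome. Infants who received LEV only or PB only are mostly those whose seizures stopped on the assigned drug. Infants who received both are those in whom it failed, from either arm. This grouping nearly restates the efficacy endpoint, because SAP 3.6 counts an infant who needs a second anticonvulsant as a failure.

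The Protocol itself supplies the reasons to expect more events among failures whatever drug they had:

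- Section 8, justifying first-line use of LEV, warns that "by studying efficacy in only those neonates who have failed to respond to a first line agent, a group of refractory neonates has been selected".
- Section 6 cites a "strong correlation between the amount of electrographic seizure activity and subsequent morbidity and mortality", and says that "20-30% of infants with neonatal seizures die".
- Section 14 lists seizures among the expected adverse events, so the trigger for the second drug may itself be counted as an event.

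An excess of events in infants given both drugs could therefore be reported with p<0.05 and read as toxicity of a drug or of the combination. LEV safety is Aim 4, and section 8 says the trial is meant to inform whether a phase III study is warranted.

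**Working it through.** SAP 7.5 states no figure to reproduce. The question is how often a drugs-received test would reject when neither drug affects safety.

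**Inputs from the documents.** 60 LEV and 40 PB infants, with response rates of 22% (LEV) and 50% (PB) (SAP 3.4). Two-sided alpha is 0.05 (SAP 6.2). As a check on these inputs, exact Fisher power for 50% against 22% with 40 and 60 infants is 79.6%, in line with the stated 80%.

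**Expected group sizes.**
- LEV only: 60 × 0.22 = 13.2
- PB only: 40 × 0.50 = 20
- Both: 60 × 0.78 + 40 × 0.50 = 46.8 + 20 = 66.8

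**Assumptions, not in the documents.** Each infant has a latent normal severity z. Event risk rises linearly with the percentile of z between two stated limits. The infant responds if ρz + √(1−ρ²) × noise falls below the 22% (LEV) or 50% (PB) cutoff. Neither drug affects event risk.

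**Worked case, risk 5–45%, ρ = 1.** Mean severity percentiles are 0.11 and 0.25 for LEV and PB responders, and 0.61 and 0.75 for failures. With risk = 5 + 40 × percentile:
- One drug: (13.2 × 9.4 + 20 × 15.0) / 33.2 = 12.8%
- Both drugs: (46.8 × 29.4 + 20 × 35.0) / 66.8 = 31.1%

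No drug effect is present, yet the rates are about 13% and 31%. At ρ = 0.5 they are 19% and 28%, and at ρ = 0.3 they are 21% and 27%.

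**Rejection rate, one drug against both (4,000 simulated trials per setting).**

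| Event risk, least to most severe | ρ = 0.3 | 0.5 | 0.7 | 1.0 |
|---|---|---|---|---|
| 10–70% | 9% | 20% | 39% | 75% |
| 5–45% | 7% | 12% | 22% | 48% |
| 1–19% | 3% | 5% | 7% | 16% |
| 2–8% | 1–2% | 1–2% | 1–2% | 1–2% |

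At ρ = 0 the test rejects in 2–4%, so the inflation comes from refractoriness alone. The randomized-arm test rejects in 1.6–4.3% across all settings. A repeat run agreed to within 2 percentage points.

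**Other readings of drugs received, at ρ = 0.3, 0.5, 1.0.**
- Three groups (LEV only, PB only, both; 2,000 trials per setting): 6%, 11%, 39% (risk 5–45%); 8%, 18%, 67% (10–70%); 2%, 2%, 5% (1–19%).
- Any LEV against PB only: 4%, 5%, 13% (5–45%); 5%, 9%, 29% (10–70%).
- LEV only against PB only: 0.1–4%, not inflated.

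**Second model.** Here response is 50% in both arms, so the groups are 30, 20 and 50, and the event rate is set directly for responders and failures.

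| Event rate, responders / failures | Both vs one drug | Three groups | Randomized arms |
|---|---|---|---|
| 25% / 25% | 4% | 5% | 4% |
| 20% / 30% | 17% | 14% | 3% |
| 15% / 35% | 60% | 51% | 4% |
| 10% / 40% | 94% | 90% | 4% |

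**The case against.** The strongest reply has five parts.

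- **The valid test is there.** SAP 7.5 names the randomized groups first and tests all four outcomes by them, so Aim 4 survives. This is true and limits the weight of the point. But the SAP does not rank the two comparisons or label one as exploratory.
- **The size rests on an unnamed contrast and unstated inputs.** One drug against both is only one reading, and another (LEV only against PB only) shows no inflation. The 48% and 75% figures need a correlation of 1.0, which is a theoretical limit. At 0.3 the corresponding rates are 7% and 9%, and for an outcome averaging about 10% or less there is little or no inflation unless the correlation is 0.7 or more. This stands as a limit on size. It does not make a p-value across response-defined groups interpretable.
- **The link to in-trial events is indirect.** The correlation cited in Protocol section 6 concerns later morbidity and mortality, not events during a short treatment course. That also bears on size only.
- **Exposure matters for safety.** At the plan's rates about 47 of 60 LEV-arm infants and 20 of 40 PB-arm infants receive both drugs, so the randomized comparison is diluted as a comparison of exposure. This is a good reason to keep the tables by drugs received, but not to test them.
- **The bias can run the other way.** An infant who dies or withdraws before a second drug is due stays in a one-drug group. The simulations omit this. It is correct, and it is a further reason why these p-values, notably for deaths and discontinuation, do not measure a drug effect.

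**Conclusion.** The concern holds for the drugs-received half of the SAP 7.5 tests. Its existence rests on the plan's own treatment sequence, together with the Protocol's description of first-drug failures as a selected, refractory group. The randomized-arm tests are unaffected.

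The size is uncertain. With no drug effect, false-positive rates for one drug against both run from no inflation (rare events or no correlation) through 7–20% (event risk 5–45% or 10–70%, correlation 0.3–0.5) to 48–75% at the limiting correlation of 1.0. These figures rest on assumed event risks and an assumed severity-response correlation. They also depend on how drugs received is defined, which the SAP leaves open. The tests should be changed, but the safety analysis as a whole is not lost.

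**What to change.** In SAP 7.5, confine the Fisher tests of AEs, SAEs, study discontinuation and deaths to the randomized groups, in line with Protocol Aim 4. Keep every table by drugs received, as description without p-values.

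Define the categories: LEV only, PB only, both, and none. The last is needed because Protocol section 10 (Group C) allows randomization during EEG set-up, before seizures are confirmed, and SAP 6.1 counts all randomized infants in the intention-to-treat population. Add a note to these tables that the groups depend on response to the first drug, and that early death or withdrawal keeps an infant in a one-drug group.

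If more detail on exposure is wanted, the record of adverse events by treatment phase (Protocol section 8, Safety data) could be used to show events by the drugs received up to onset, again descriptively.

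The cost is SAP wording only. No table, data item or planned randomized comparison is lost.
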